6.9. Ordinal Scale

The ordinal scale is an assessment of the clinical status at a given study day. Each day, the worst (i.e. lowest ordinal) score from the previous day will be recorded. i.e. on Day 3, the lowest ordinal score from Day 2 is obtained and recorded for Day 2. The scale is as follows:

1. Death
2. Hospitalized, on invasive mechanical ventilation or ECMO
3. Hospitalized, on non-invasive ventilation or high flow oxygen devices

4. Hospitalized, requiring low flow supplemental oxygen
5. Hospitalized, not requiring supplemental oxygen - requiring ongoing medical care (COVID-19 related or otherwise)
6. Hospitalized, not requiring supplemental oxygen - no longer requires ongoing medical care (other than per protocol RDV administration)
7. Not hospitalized

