8.5. Efficacy Analysis

8.5.1. Primary Analysis

The primary endpoint will be analyzed using a proportional odds model. The null hypothesis being tested is whether the odds of improvement on the ordinal scale is the same for the two treatment groups (ie, whether the common odds ratio is equal to 1). The odds ratio and 95% confidence interval will be provided.

The proportion of subjects in each category will be summarized by treatment group. The validity of the proportionality assumption will be evaluated.

If a participant is discharged prior to Day 14, the Day 14 ordinal scale category is considered to be not hospitalized. Every effort will be made to obtain clinical status data for all subjects prior to discharge. Subjects who have missing clinical status information on Day 14 will be excluded from the primary analysis.

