2.1.2. Primary Analysis

The primary analysis was performed after participants in Part A either completed 14 days or prematurely terminated from Part A on or prior to Day 14.

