6. EFFICACY ANALYSES

6.1. Primary Efficacy Endpoint

The primary efficacy endpoint was analyzed for Part A of the study and is not described in this SAP.

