6.2. Efficacy Endpoints of Interest

Efficacy endpoints of interest include endpoints based on clinical status assessed by a 7-point ordinal scale. The endpoint will be derived by combining the available death, hospital discharge alive and ordinal scale assessment reported by the site, where death supersedes discharge alive and discharge alive supersedes the ordinal scale score reported by the site.

Sites were instructed to report the worst ordinal scale category for each day. Therefore, the ordinal scale result on the day the participant was discharged alive does not necessarily reflect Not hospitalized (7). The definition of clinical status based on the 7-point ordinal scale is defined as follows:

- If a participant dies while hospitalized (as recorded on the Death eCRF and Hospitalization eCRF), the endpoint on the day of death and all subsequent days through Day 28 will be set to Death (1)
- If the participant is discharged alive, the endpoint on the day of discharge alive and all subsequent days through Day 28 will be set to Not hospitalized (7)
- If the participant is discharged alive and dies on the same day or a later day (as recorded on the Death eCRF and Hospitalization eCRF), the endpoint on the day of discharge alive and all subsequent days until the day of death will be set to Not hospitalized (7). On the day of death and all subsequent days through Day 28, the endpoint will be set to Death (1),

Every effort will be made to obtain clinical status data for all participants prior to discharge alive. The last known clinical status will be used for days with missing clinical status (eg, where the reason for Hospital Discharge is not “Discharged Alive” and the participant has not died). All post-baseline days with missing ordinal scale score, from Day 2 to Day 14 and Day 28, will use the previous last known clinical status.

Efficacy endpoints of interest include

- Clinical status on Days 1 to 14, Day 28 and last available assessment
- Change in clinical status on Days 5, 7, 11, 14, 28, and last available assessment
- Time to clinical improvement (days): Clinical improvement is defined as a ≥ 2 -point improvement from baseline clinical status or discharged alive on the 7-point ordinal scale using the definition specified above.

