6.3. Changes from Protocol-Specified Efficacy Analyses

There are no changes from the protocol-specified efficacy analyses.

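### Protocol 8.5.1 scores every participant discharged before Day 14 as not hospitalized and, as worded, makes no exception for death after discharge and by Day 14

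*Protocol*

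**What the plan says.** Protocol 8.5.1 fits a proportional odds model to the 7-point scale on Day 14 and also requires a category table: "The proportion of subjects in each category will be summarized by treatment group". For early discharge its rule is: "If a participant is discharged prior to Day 14, the Day 14 ordinal scale category is considered to be not hospitalized". The only other data-handling rule there excludes participants whose Day 14 status is missing. It does not mention death.

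Protocol 6.9 describes the scale this way: "The ordinal scale is an assessment of the clinical status at a given study day". Category 1 is death, with no in-hospital qualifier, and category 7 is not hospitalized.

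The supplied SAP covers Part B. Its section 6.2 sets an order of precedence: "death supersedes discharge alive and discharge alive supersedes the ordinal scale score reported by the site". It then says that a participant who dies after being discharged alive is scored 7 until the day of death and 1 from that day through Day 28. On Part A, SAP 6.1 says: "The primary efficacy endpoint was analyzed for Part A of the study and is not described in this SAP". SAP 6.3 adds: "There are no changes from the protocol-specified efficacy analyses".

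**The concern.** Take a participant discharged on Day 6 who dies on Day 12. Their clinical status on Day 14 is death, category 1. The early-discharge sentence gives category 7, because the participant was discharged before Day 14 and the sentence carries no other condition. Reading discharged as discharged alive does not help, since this participant was alive at discharge.

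No other visible protocol text overrides the sentence. Daily scoring in Protocol 6.3 stops at discharge. The Day 28 telephone review in Protocol 6.5 covers the ordinal scale only for those discharged on or after Day 14. For anyone discharged earlier and followed by telephone, the sentence in 8.5.1 is therefore what fixes the Day 14 score.

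At stake are the primary odds ratio, if such deaths are unevenly spread between arms, and the death row of the category table, even if they are evenly spread. Deaths in hospital are not affected. The deaths are not lost to the trial, because all-cause mortality at Day 28 is an endpoint of interest in Protocol 3.1.

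**Working it through.** **1. Planned power reproduces.** Inputs from Protocol 8.9: 400 participants allocated 1:1, odds ratio 1.75, two-sided 0.05, and a Group 1 (5-day) distribution of 2, 4, 7, 13, 16, 20 and 38% for categories 1 to 7. Shifting this by 1.75 gives 1.15, 2.37, 4.35, 8.85, 12.55, 18.98 and 51.75% for Group 2 (10-day). The averaged proportions give 1 − Σp̄³ = 0.8978.

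- θ = ln 1.75 = 0.5596
- √(400 × 0.8978 / 12) = 5.4705
- Power = Φ(0.5596 × 5.4705 − 1.960) = Φ(1.101) = 86.5%

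This agrees with the stated power above 85%. Moving 1, 2 or 4 of the 200 Group 1 participants from category 7 to category 1, with the odds ratio held at 1.75, gives 86.6, 86.7 and 86.9%. Planned power is not the issue.

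**2. Effect on the odds ratio.** The documents give no rate of death after discharge, so every count below is an assumption. The starting table is what the rule would report: 4, 8, 14, 26, 32, 40 and 76 participants in the 5-day arm (200 × the planning percentages), and either the same counts or the counts shifted by 1.75 in the 10-day arm. The assumed deaths are then moved from category 7 to category 1 and the proportional odds model is refitted by maximum likelihood. The odds ratio is 10-day relative to 5-day.

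| Assumed deaths, 5-day / 10-day | Reported under the rule | Deaths scored 1 |
|---|---|---|
| 1 / 0 | 1.00 | 1.026 |
| 0 / 1 | 1.00 | 0.975 (0.9746 before rounding) |
| 4 / 2 | 1.00 | 1.053 (95% CI 0.74 to 1.49) |
| 2 / 4 | 1.00 | 0.950 (95% CI 0.67 to 1.35) |
| 1 / 1, 2 / 2 or 4 / 4 | 1.00 | 1.000 |
| 1 / 1 | 1.75 | 1.743 |
| 2 / 2 | 1.75 | 1.736 |
| 4 / 4 | 1.75 | 1.723 |
| 4 / 0, 10-day counts rounded to whole participants | 1.73 | 1.91 |
| 0 / 4, 10-day counts rounded to whole participants | 1.73 | 1.55 (95% CI 1.08 to 2.22) |

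At a reported odds ratio of 1.00 the standard error of the log odds ratio is 0.180. One death in one arm only therefore moves the estimate by ln 1.026 / 0.180 = 0.14 standard errors, and by the same amount in the other direction. The last two rows are the extreme: four deaths, all in one arm. For 0 / 4 the shift is ln(1.73 / 1.55) = 0.110. With a standard error of ln(2.48 / 1.20) / 3.92 = 0.185, taken from the 95% CI of 1.20 to 2.48 around 1.73, that is about 0.6 standard errors.

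Four in one arm is a generous assumption. It equals the whole planned number of Day 14 deaths in the 5-day arm (2% of 200 = 4), and is 4 / 76 = 5.3% of those planned to be out of hospital. The 76 may also include participants discharged on Day 14 itself, whom the sentence does not cover.

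**3. Effect on the death row.** One participant in 200 is 0.5 percentage points. Each such death scored 7 lowers the death row by that amount in its arm and raises the not-hospitalized row equally, whatever the balance between arms. For example, if the planned 2% (4 of 200) is total Day 14 mortality and one of those four died after discharge, the row would show 3 / 200 = 1.5%.

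**The case against.** The best defence is that the sentence only fills a gap. Scoring stops at discharge, so without it everyone who went home early would have no Day 14 score and would be excluded as missing. A known death is a known status, and category 1 is death wherever it occurs. The Part B SAP supports this reading: it is based on protocol Amendment 3.0, gives death precedence, and still declares no change from the protocol's efficacy analyses. This is fair evidence of intent. It does not repair 8.5.1, because the same SAP leaves the Part A primary endpoint out and no visible protocol text supplies the exception.

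A reader might go further and infer that Part A was misscored. The documents do not support that. No Part A SAP is supplied, the text of Protocol 8.1 is not in the extract, and Protocol 8.3.2 opens with a redaction. Any of these could hold a precedence rule, and none can be counted as missing from the plan.

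A reader might also infer a bias towards one regimen. Nothing gives the direction: counts of death after discharge are not reported and may be zero in both arms.

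Nor do the documents establish an error for participants readmitted by Day 14. SAP 6.2 enters COVID-19 readmissions under the latest admission, and the scoring of other readmissions is not settled.

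The objection that the effect is very small stands, and it is why this is a minor point.

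**Conclusion.** The point holds as a defect in the wording of Protocol 8.5.1. It is a stated rule that, followed exactly, puts a death in the best category of the primary endpoint. It is not a finding about the Part A results.

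The size rests on assumed counts and the planning distribution. One such death in one arm only shifts a reported odds ratio of 1.00 to 1.03 or 0.97, about 0.14 standard errors, and four per arm shift 1.75 to 1.72. Only a heavily one-sided count would move the estimate visibly. The category table is the more certain casualty, at 0.5 percentage points of the death row per death. Severity is minor.

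**What to change.** State in Protocol 8.5.1 that death on or before Day 14, in or out of hospital, is category 1 and overrides discharge. This matches the order the sponsor already uses in SAP 6.2.

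That sentence cannot change work already done. According to SAP 2.1.2, "The primary analysis was performed after participants in Part A either completed 14 days or prematurely terminated", and SAP 2.1.3 describes the Part A final analysis as performed too. The study report should therefore give, by arm, the number of participants discharged before Day 14 who had died by Day 14, and say how they were scored. If there were none, or all were scored 1, a statement to that effect closes the matter. If any were scored 7, rescore them as 1 and rerun the proportional odds model and the category table.

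The cost is one sentence, one two-arm count and, at most, one rerun of an existing model and table. No new data are needed: death is a seriousness criterion in Protocol 7.1.2, and Protocol 7.3.3 requires serious adverse events to be reported throughout the study, including follow-up.

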8.5.2. Secondary Analyses

The secondary endpoint of proportion of participants with treatment emergent AEs will be compared between the 2 treatment groups in Part A using a Fisher's Exact test. The point estimate of the treatment difference and the associated 95% confidence intervals will be provided. Secondary or other endpoints of interest related to proportion of participants will be compared between treatment groups in Part A using a chi-square test or Fisher's Exact test. Endpoints that are measured as time to first event will be compared between treatment groups using the Log-Rank test and continuous endpoints will be compared between treatment groups using a Wilcoxon rank sum test or analysis of variance model.

For Part B, summaries of the 7-point scale ordinal scale and other efficacy endpoints of interest will be provided by group (Mechanically Ventilated Treatment Group or Extension Treatment Group).

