3.1. Endpoints

The primary endpoint of this study is:

- Clinical status assessed by a 7-point ordinal scale on Day 14

The secondary endpoint of this study is:

- The proportion of participants with treatment emergent AEs

Other endpoints of interest are:

- Time to SpO₂ > 94% on room air
- Time to first negative SARS-CoV-2 polymerase chain reaction (PCR)
- Duration of oxygen therapy (days)
- Duration of hospitalization (days)
- All cause mortality at Day 28
- Time to clinical improvement (days): Clinical improvement is defined as a \geq 2-point improvement from Day 1 on a 7-point ordinal scale

- The proportion of participants in the Mechanically Ventilated Treatment Group and Extension Treatment Group with treatment-emergent AEs

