3.4. Duration of Treatment

Participants will receive study treatment with RDV for 5 days (Treatment Group 1), 10 days (Treatment Group 2), 10 days (Mechanically Ventilated Treatment Group), or either 5 or 10 days (Extension Treatment Group). If the participant is discharged, RDV treatment will stop at that time.

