4. SUBJECT POPULATION

4.1. Number of Subjects and Subject Selection

In Part A, approximately 400 participants will be randomized in a 1:1 ratio into 1 of 2 treatment groups. In Part B, up to approximately 5600 participants may be assigned to 1 of 2 treatment groups. Rescreening may occur at the investigator's discretion.

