8.9. Sample Size

The sample size computation is based on an assumed distribution of the 7-point ordinal scale on Day 14 for Part A Treatment Group 1. The odds ratio represents the odds of improvement in the ordinal scale for Treatment Group 2 relative to Treatment Group 1. The sample size needed to detect a given odds ratio for a 1:1 randomization using a 2-tailed test at level α is given by:

$$12 (z_{\alpha/2} + z_{\beta})^2 / \theta^2 (1 - \sum_{i=1}^7 \rho_i^3)$$

Where θ is the log odds ratio, ρ_i is the overall probability (combined over both treatment groups) of being in the i th category of the ordinal outcome, and $z_{\alpha/2}$ and z_{β} are the $1 - \alpha/2$ and β quantiles of the standard normal distribution {Whitehead 1993}.

A sample size of 400 participants (200 in each group) achieves > 85% power to detect an odds ratio of 1.75 using a two-sided significance level of 0.05. In this sample size calculation, it is assumed that the probability distribution of the ordinal scale at Day 14 for Group 1 is as follows:

1. Death, 2%
2. Hospitalized, on invasive mechanical ventilation or ECMO, 4%

3. Hospitalized, on non-invasive ventilation or high flow oxygen devices, 7%
4. Hospitalized, requiring low flow supplemental oxygen, 13%
5. Hospitalized, not requiring supplemental oxygen - requiring ongoing medical care (COVID-19 related or otherwise), 16%
6. Hospitalized, not requiring supplemental oxygen - no longer requires ongoing medical care (other than per protocol RDV administration), 20%
7. Not hospitalized, 38%

The sample size calculation was done using software PASS (Version 14.0).

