- Percentage of participants with a ≥ 2 -point improvement or discharged alive based on the 7-point ordinal scale using the definition specified above on Day 5, Day 7, Day 11, Day 14, Day 28, and last available assessment

- Time to ≥ 1 -point improvement (days) from baseline clinical status on the 7-point ordinal scale using the definition specified above.
- Percentage of participants with a ≥ 1 -point improvement based on the 7-point ordinal scale using the definition specified above on Day 5, Day 7, Day 11, Day 14, Day 28 and last available assessment
- Time to recovery based on the 7-point ordinal scale using the definition above, where recovery is defined as an improvement from a baseline score of 2 through 5 to a score of 6 or 7, or an improvement from a baseline score of 6 to a score of 7
- Percentage of participants with recovery based on the 7-point ordinal scale using the definition specified above on Day 5, Day 7, Day 11, Day 14, Day 28 and last available assessment
- Number of days of oxygen support while hospitalized through discharge alive, death or Day 14 based on the 7-point ordinal scale reported values (See [Appendix 2](#)). This summary will present results separately for participants who died on or prior to Day 14 and those who were discharged alive on or prior to Day 14 and will include:

Days on invasive mechanical ventilation

Days on high flow oxygen devices

Days requiring low flow supplemental oxygen

Because oxygen support status was collected only while the participant was in the hospital, if a participant was discharged alive and died afterwards, the participant will be included only in the summary for participants discharged alive.

- Shift in oxygen support status from baseline to Days 5, 7, 11, 14, 28 and last available assessment
- Duration of hospitalization (days) (duration from hospital admission and duration from Day 1). Duration of hospitalization is calculated through Day 28 for participants who were discharged alive on or prior to Day 28. If participants were rehospitalized for COVID-19 related reasons, the hospitalization discharge information is entered in the eCRF database using the latest hospitalization admission.
- All-cause mortality

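### If discharge-ready participants in the 10-day arm of Part A are kept in hospital for doses, the planned comparison of hospital stay partly measures the dosing schedule and favours the 5-day arm

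*Protocol*

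**What the plan says.** Part A compares 5 with 10 days of IV remdesivir. Protocol 4.1: "In Part A, approximately 400 participants will be randomized in a 1:1 ratio into 1 of 2 treatment groups". Assignment is open label (Protocol 5.1.2).

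Dosing is tied to the inpatient stay. Protocol 3.4: "If the participant is discharged, RDV treatment will stop at that time"; Protocol 5.3 repeats the rule. The scale in Protocol 6.9 allows for people who remain in hospital while dosing continues. Category 6 is hospitalized, off oxygen, and "no longer requires ongoing medical care (other than per protocol RDV administration").

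Protocol 3.1 lists duration of hospitalization among the other endpoints of interest, together with "Time to clinical improvement (days): Clinical improvement is defined as a" gain of at least 2 points from Day 1. Protocol 8.5.2 assigns the tests in one sentence. Its first half is "Endpoints that are measured as time to first event will be compared between treatment groups using the Log-Rank test", which covers time to improvement. Its second half gives continuous endpoints, and so hospital stay, a Wilcoxon rank sum test or analysis of variance. Protocol 8.8 plans no multiplicity adjustment.

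The SAP supplied covers Part B only (SAP 1 and 6.1). For Part B it already has an endpoint suited to this problem: "recovery is defined as an improvement from a baseline score of 2 through 5 to a score of 6 or 7", or from 6 to 7 (SAP 6.2), analysed with death as a competing risk (SAP 6.2.1).

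**The concern.** Take two participants who become fit to leave on Day 6, one in each arm. The 5-day participant has finished dosing and can go home. The 10-day participant can also go home, but then forgoes the remaining doses; completing the course means staying to Day 10. Whoever makes that choice knows the arm. To the extent that sites choose completion, the 10-day arm stays longer with no difference in disease course.

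Part A exists to choose a duration (Protocol 1.3), and treatment in the Part B Extension group may be shortened after the Part A data are analysed (Protocol synopsis). A shorter stay produced by the schedule could then be taken as faster recovery on 5 days. The protocol contains no caveat or sensitivity analysis for this.

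**Working it through.** **1. The plan's own figure.** Protocol 8.9: "A sample size of 400 participants (200 in each group) achieves > 85% power to detect an odds ratio of 1.75". The test is two-sided at 0.05. Take θ = ln 1.75 = 0.560 and the assumed Group 1 shares 2/4/7/13/16/20/38%. The Group 2 shares implied by the odds ratio are 1.2/2.4/4.4/8.9/12.6/19.0/51.8%. With ρ the average of the two arms, 1 − Σρ³ = 0.898. For 85% power, N = 12(1.960 + 1.036)² / (0.560² × 0.898) ≈ 383, and power at N = 400 is 86.5%. The stated figure is reproduced. It concerns the Day 14 primary endpoint only; no power or error rate is given for hospital stay.

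**2. The most one participant can be delayed.** A 10-day participant ready on Day 9 and held to Day 10 stays 10 − 9 = 1 extra day; one ready on Day 5 stays 10 − 5 = 5.

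**3. Hospital stay under equal recovery.** Assumptions not in the documents: time to discharge readiness is lognormal (log-SD 0.65), rounded up to whole days and limited to 2-29. In the 10-day arm, readiness on Days 5-9 moves to Day 10 for a stated share. There are 200 per arm, all 400 are analysed, and the test is a two-sided 0.05 Wilcoxon. Two settings were used:

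- Median 12.5 days: 57% home by Day 14, 27% ready on Days 5-9.
- Median 14 / exp(0.65 × −0.305) = 17.1 days: 38% home by Day 14, the protocol's own figure for Group 1, and 15% ready on Days 5-9.

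| Home by Day 14 | None held | Half held | All held |
|---|---|---|---|
| 38% | 4% | 5-6% | 8% |
| 57% | 4-5% | 11-12% | 31-35% |

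Ranges are over repeated runs of 2,000 to 4,000 trials. In the 57% setting the mean excess stay is 0.3-0.4 days (half held) and 0.7 days (all held), and the share home by Day 7 is 19% in the 5-day arm against 11% or 4%. If only those discharged by Day 28 are analysed, rejection in that setting is 13-15% and 42-43%.

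**4. Sensitivity to the model.** A second model used exponential readiness times (38%, 58% or 75% ready by Day 14). Anyone ready before the last scheduled dose could be held, and only those discharged by Day 28 were analysed. Significant results favouring 5 days (nominal 2.5%) were 9-26% with a quarter held, 22-84% with half and 80-100% with all. Mean excess stay was 0.4-0.7, 0.8-1.3 and 1.7-2.6 days. This model puts more readiness before Day 10, so more people can be held. The direction is the same in both models, but the size is set by assumption.

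**5. Time to a 2-point improvement.** Part A excludes ventilated participants (Protocol 3.3). The target by baseline category is:

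- 3 → 5 and 4 → 6: both reachable in hospital during dosing.
- 5 → 7: requires discharge.
- 6 → 8: does not exist.

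Only baseline 5 is directly affected. Protocol 4.2 admits such people (SpO₂ at or below 94% on room air), but the baseline mix is not given. Under the model in step 4, with a log-rank test, significant results favouring 5 days (nominal 2.5%) are:

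| Share at baseline 5 | Half held | All held |
|---|---|---|
| 10% | 3-4% | 3-4% |
| 30% | 3-6% | 4-15% |
| 50% | 3-12% | 5-41% |

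**6. Counting readiness instead of discharge.** If the event is reaching 6 or 7, holding for doses does not delay it, and the model in step 4 returns 2.1-3.0% against 2.5%. This assumes category 6 is scored alike in both arms.

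**The case against.** Nothing in the protocol requires anyone to stay for doses. Protocol 3.4 and 5.3 end treatment at discharge, and Protocol 6.11.1 lists discharge as a reason to stop. A reader might infer that the 10-day arm is bound to look worse. The documents do not support that: it follows only if some discharge-ready participants are held. This stands, and the point is conditional.

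A reader might also infer that time to improvement is distorted in general. It is not: from baseline 3 or 4 the target can be reached while dosing continues, because category 6 sets study-drug administration aside.

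A longer stay may also be a genuine consequence of the longer schedule. Protocol 1.4 names benefit to patients and society from finding the minimum effective duration. This stands too. Raw stay is a legitimate outcome under the assigned regimen; the error would be to read it as speed of recovery.

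Nor are early discharge and prolonged stay inseparable. Daily scores (Protocol 6.3 and 6.9) and exposure by group (Protocol 8.6.1) show which occurred.

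Finally, these endpoints rank below primary and secondary, no text ties the choice of regimen to hospital stay, and a Part A SAP, not among the documents, may already deal with the matter. This limits the weight of the point but does not remove it.

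**Conclusion.** The concern holds in a limited, conditional form. The differing inpatient requirement is in the protocol, the direction is clear, and the protocol plans no safeguard for hospital stay. The size depends on the share held and on discharge timing, both assumed here. With all participants analysed, two-sided rejection under equal recovery runs from about 5-8% (38% home by Day 14) to 11-35% (57% home), for half to all held. It is higher if only those discharged by Day 28 are analysed, and nominal if nobody is held.

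The effect on time to improvement is minor unless baseline category 5 is a large share. The primary endpoint should not be drawn into this: Day 14 falls after the last scheduled dose in both arms.

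**What to change.** Keep the planned endpoints and add three things for Part A:

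- A between-arm analysis of time to first score of 6 or 7 (7 if baseline is 6), with death as a competing event, using the recovery definition in SAP 6.2.
- Days in categories 2-5 and days in category 6, by arm, through the scheduled dosing period. Category 6 should not be labelled as stay only for remdesivir: Protocol 8.9 expects 20% of the 5-day group there on Day 14, which is 14 − 5 = 9 days after their last scheduled dose.
- A statement that raw duration of hospitalization describes resource use under the assigned schedule and is not evidence of faster recovery.

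The cost is wording and a derivation from scores already collected (daily to Day 14, then changes to discharge or Day 28 under Protocol 6.5). SAP 2.1.3 reports that the Part A final analysis has been done, so unless the Part A plan already contains this analysis it should be labelled supplementary.

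The downside is that the boundary between 5 and 6 is a judgement made with knowledge of the arm. The added analysis therefore supports the planned endpoints and does not replace them.
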